Comprehensive assessments will be conducted at baseline and repeated at two months (end of active phase), and four months (two-month follow-up from end of active phase). An additional assessment for the primary outcome (SFS) and hypothesized moderator (USS Skills Test) will occur at one month (midpoint through the active phase). Participants will be oriented to the EMA procedures during the baseline assessment. This will include practice with receiving EMA survey links, navigating the questionnaires, and a comprehension check of survey questions and responses. Smartphones will be given to participants so that they can complete these EMA surveys. In addition to the smartphones, a data plan will be provided for 6-months or until study completion. Participants will then be provided with instructions for how to transfer the phone service into their name if they wish to keep the phone. For participants who are terminated for cause or decide to withdraw from the study, the dataplan will be terminated and the phone will be locked to prevent it being used to obtain a new wireless service plan. Orientation, including basic use and charging of the smartphone will be provided when the phones are given out. We anticipate that length of study participation for individual participants will be approximately 5 months.

Procedures for normative psychiatric (non psychotic) sample: Following written informed consent and baseline screening assessment using measures described above (approximately 90 min session), participants who continue to meet all eligibility criteria will be oriented to the EMA procedures. This will include practice with receiving EMA survey links, navigating the questionnaires, and a comprehension check of survey questions and responses. Participants will be asked to save to their contacts the telephone number from which the surveys originate. Next, over the course of 7 days they will receive 4x/day brief surveys about their social interactions. Survey questions are the same as for the psychosis spectrum sample. Length of study participation for the normative sample is approximately 7 days (baseline screening assessment plus 7 days of EMA assessments).

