Justification of Sample Size: The primary hypothesis is that USS will result in greater total SFS scores immediately following training (i.e. 'post' assessment) compared to control. We have powered our study to detect what we consider a clinically meaningful, moderate effect on this measure. Given the following: 1) power of 90%, 2) a two-sided 0.05 significance level, 3) a standard deviation for total SFS score of 13.1 (from our preliminary data), and 4) a 1:1 intervention allocation, a sample size of 46 subjects per group will be required to detect a 9 point difference (i.e. moderate effect size $d=0.69$) between USS and control in total SFS score at the post assessment. Please refer to Figure, showing the power to detect different effect sizes in total SFS given this sample size. A total of 120 participants will be enrolled and randomized to accommodate up to 20% dropout.

While inherently difficult to define as it varies by perspective (e.g. researcher, consumer, insurance company)⁸², we settled on moderate ES on SFS as clinically meaningful based on past social cognitive studies that used the SFS and noted that improvement in social relationships (more friends, less time spent alone, higher quality of social communication) were observed with small-medium effect sizes⁸³. Small-medium effects on the SFS have also been related to greater social acceptability by peers, better overall social skills ability, and higher medication compliance, with effects greater than 0.50 on social cognitive measures distinguishing between patients with psychosis and higher functioning patients with bipolar disorder⁸⁴. Perhaps the most striking example of the real-world significance of change on the SFS comes from the original SFS validation study, wherein 11 point difference separated those who were employed from those who were not⁷³.

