Analysis of Primary Outcome SFS (Aim 1): The primary objective of the analysis is to demonstrate that USS will improve social functioning at the end of training more than active control in participants with PSD and impaired social functioning. The primary outcome (total scores on the SFS) will be assessed prior to initiation of intervention (pre), the training mid-point (mid), the end of training (post) and 2 months following the end of training (FU). Likelihood-based ignorable analysis using a linear mixed model will be used to compare social functioning between groups^{85, 86}. The primary advantage of the repeated measures linear mixed model when compared to commonly used methods such as complete case analysis and single imputation (e.g. last observation carried forward) is its flexibility in handling missing data. This analysis will assume that missing data occurs at random (i.e. MAR, not informative). The inclusion of pre, mid and FU outcome data in the model will assist in meeting this assumption. Furthermore, we will evaluate patterns of missing data as well as determine baseline characteristics that are predictive of dropout. If identified, these characteristics will be included in the model to meet the MAR assumption. The mixed model will include fixed effects for intervention (USS vs. active control), time (mid, post, FU), and the interaction of intervention with time. An additional fixed effect will be included for baseline SFS at pre. An unstructured covariance pattern will be used to accommodate correlation from repeated measures. A linear contrast will be used to estimate intervention group differences and 95% confidence intervals at the post assessment.

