Analysis of Real World Social Behaviors (Aim 2): Ecological momentary assessment (EMA) analyses will be conducted using a multilevel modeling approach⁸⁷. Analyses handle data estimation with a restricted maximum likelihood approach. Data will be organized hierarchically, with within-person/random EMA prompts across the study period nested within people. Random (within-person) coefficients will be estimated for each person at Level 1, while fixed (between-person) coefficients will be estimated at Level 2. Within-person variables will be centered at Level-1 and between-person variables will be grand mean centered at Level-2⁸⁸⁻⁹⁰. We will examine associations between [e.g., attributions] and [e.g., number of interactions] at Level 1, and fit models with fixed [e.g. group, age, gender] main effects at Level 2. We will also examine [L1] and [L2] cross-level interactions.

Analysis of Social Interaction Skills (Aim 3) and Durability (Aim 4): The secondary outcome social interaction skills, assessed by SSPA, will be compared between USS and control using a repeated measures linear mixed model similar to that described in the analysis of the primary outcome. Durability will also be compared between USS and control using the mixed model. For primary and secondary outcomes, linear contrasts will be used to estimate intervention group differences and 95% confidence intervals at the 2-month FU assessment.

Analysis of Mediation (Exploratory Aim A): We will explore content learning (USS Skills Test) as a potential mediator of the relation between intervention and changes in social functioning. Direct and indirect effects will be estimated using a structural equation model. Mediation (i.e. indirect effects) will be tested using the bootstrapping approach⁹¹.

Analysis of Moderation (Exploratory Aim B): Heterogeneity of treatment effects (HTE) for the primary outcomes will be explored in subgroups of participants based on baseline characteristics including cognition, symptom clusters, illness characteristics, medication dose (chlorpromazine equivalents) and demographic variables. These subgroup analyses are aimed at determining whether there is differential effectiveness of the interventions among participant subgroups. Evidence of HTE will be based on tests of interaction within the longitudinal model structure described above.

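### The SFS model uses one baseline slope for all three visits; if the slope changes over time, the follow-up contrast for Aim 4 is reported with up to about 11% too much variance

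*Combined protocol and SAP*

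**What the plan says.** The Statistical Analysis Plan, under Analysis of Primary Outcome SFS (Aim 1), lists "fixed effects for intervention (USS vs. active control), time (mid, post, FU), and the interaction of intervention with time". It then adds the baseline: "An additional fixed effect will be included for baseline SFS at pre". On the residuals it says "An unstructured covariance pattern will be used to accommodate correlation from repeated measures". The primary result comes from one contrast: "A linear contrast will be used to estimate intervention group differences and 95% confidence intervals at the post assessment".

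Under Social Interaction Skills (Aim 3) and Durability (Aim 4), the mixed model is used again. For primary and secondary outcomes, "linear contrasts will be used to estimate intervention group differences and 95% confidence intervals at the 2-month FU assessment". The SSPA gets a "repeated measures linear mixed model similar to that described in the analysis of the primary outcome".

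The procedures section places mid, post and follow-up at one, two and four months. The assessment timeline shows SFS at all of these visits, but SSPA only at baseline, post and follow-up. The randomization section stratifies on baseline SFS without giving the cut points. No baseline-by-time term appears anywhere, and no reason is given for a constant slope.

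**The concern.** A score taken before training often predicts a one-month score better than a four-month score. With a single coefficient, the fitted slope is a weighted compromise, usually close to the mid-point slope because residual variance is smallest there. At follow-up the model may then adjust too strongly for baseline. The misfit goes into the residual variance at that visit, and so into the standard error of the follow-up contrast.

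The unstructured covariance does not prevent this. It frees the variances and correlations of the residuals but leaves the mean model, where the constraint sits, unchanged.

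At stake is some precision on the durability contrast of Aim 4 and, to a much smaller degree, on the primary contrast at post.

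**Working it through.** **The plan's own figure.** Justification of Sample Size uses a 9-point difference, SD 13.1, 90% power, "a two-sided 0.05 significance level" and 1:1 allocation. The normal approximation gives 2 × (1.960 + 1.282)² × (13.1/9)² = 44.5, so 45 per group. The noncentral t gives 46 (power 0.903), which matches the plan. With 120 randomized and 20% lost, 96 remain. That calculation uses the unadjusted SD at post, so this point does not touch it.

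**Formula.** Take complete data, unstructured covariance and a full intervention-by-time mean. Let b be the vector of true baseline slopes at mid, post and follow-up, and S the covariance of the three scores given baseline, with baseline variance set to 1. In large samples:

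- common slope: b_c = 1'S⁻¹b / 1'S⁻¹1
- variance ratio at visit t, common slope over baseline-by-time: 1 + (b_t − b_c)² / S_tt

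**Inputs.** All slopes and correlations below are assumed. The SD is equal at every visit unless stated, so that slope equals correlation with baseline. Here r is the correlation between any two later visits.

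| Assumed pattern | Slopes mid/post/FU | b_c | Ratio at post | Ratio at FU |
|---|---|---|---|---|
| Constant slope | 0.70/0.70/0.70 | 0.700 | 1.000 | 1.000 |
| Mild fall, r = 0.7 | 0.70/0.65/0.60 | 0.661 | 1.000 | 1.006 |
| Mild fall, r = 0.75 | 0.75/0.70/0.65 | 0.714 | 1.000 | 1.007 |
| Moderate fall, r = 0.7 | 0.70/0.60/0.50 | 0.643 | 1.003 | 1.027 |
| Moderate fall, r = 0.7 | 0.80/0.70/0.60 | 0.750 | 1.005 | 1.035 |
| Same, r = 0.8 | 0.80/0.70/0.60 | 0.778 | 1.012 | 1.049 |
| Autoregressive by visit, 0.8 | 0.800/0.640/0.512 | 0.741 | 1.017 | 1.071 |
| Autoregressive by month, 0.9 | 0.900/0.810/0.656 | 0.874 | 1.012 | 1.083 |
| Autoregressive by month, 0.8 | 0.800/0.640/0.410 | 0.715 | 1.010 | 1.112 |

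One row in full (autoregressive by visit, 0.8): the weights on the three slopes are 0.778, 0.037 and 0.185. So b_c = 0.778 × 0.800 + 0.037 × 0.640 + 0.185 × 0.512 = 0.741. At follow-up S_tt = 1 − 0.512² = 0.738, and the ratio is 1 + (0.512 − 0.741)²/0.738 = 1.071.

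**Slope against correlation.** The model constrains slopes. Take correlations 0.80/0.70/0.60 with r = 0.7, but let the SD be 1.0, 1.1 and 1.2 times baseline. The slopes become 0.80/0.77/0.72 and b_c is 0.791. The follow-up ratio drops from 1.035 to 1 + (0.72 − 0.791)²/0.922 = 1.005.

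**Finite samples.** Simulation with 60 per arm, 20% dropout completely at random and 600 trials per setting gave these follow-up standard errors:

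- Constant correlation 0.7: 1.882 (common slope) and 1.887 (baseline-by-time), variance ratio 0.994. The unneeded term costs about 0.5%.
- 0.75/0.70/0.65: 1.992 and 1.989, ratio 1.003.
- 0.80/0.70/0.60: 2.118 and 2.073, ratio 1.044.
- Autoregressive by visit, 0.8: 2.318 and 2.241, ratio 1.070. The 95% interval is 2 × 1.96 × 2.318 = 9.09 points wide instead of 8.78.

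**Stratification.** A misfitted slope adds real sampling error only through chance baseline imbalance between arms. If strata were a median split of a normal score, 1 − 2/π = 0.36 of that imbalance variance would remain. The true ratio in the autoregressive 0.8 case would then be about 1 + 0.36 × 0.071 = 1.026. Simulation of that case gave 1.02 with stratification and 1.06 without, with noise of a few percent. The model-based ratio stayed at 1.072.

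**SSPA.** With only post and follow-up, and a correlation of 0.8 between them, slopes of 0.70/0.60 give a follow-up ratio of 1.007, and 0.60/0.50 give 1.005.

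**The case against.** The strongest reply is that nothing here is wrong. A single baseline covariate with unstructured covariance is a coherent, pre-specified model. The size of the loss depends on correlations that the documents do not report, and nothing in them favours a steep fall. Stratification removes much of the real loss. Even in the autoregressive 0.8 case, power for 9 points at follow-up is about 97% with the common slope (9/2.318 − 1.96 = 1.92) and 98% with the added term (9/2.241 − 1.96 = 2.06). All of this stands, and it sets the rank of the point. It does not remove the point, because the constraint is in the text, is given no reason and is cheap to lift.

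Four stronger readings are tempting and are not supported:

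- **The added term always lowers the variance.** It does so only if slopes differ between visits; otherwise it costs about 0.5%.
- **The primary contrast loses materially.** Inflation of 3 to 5% at post needs steep assumed falls between visits that the documents do not suggest. The patterns above give at most 1.017.
- **The treatment estimate is biased.** No bias was seen under completely random dropout. A shift needs both unequal slopes and dropout that depends on baseline SFS differently by arm. With such dropout in one arm only, an assumed case moved the follow-up estimate by about 0.3 to 0.5 points, against a 9-point target. The documents give no reason to expect that pattern.
- **SSPA is affected equally.** It has no mid-point visit, and its model is only described as similar to the primary one.

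**Conclusion.** The point holds as a minor efficiency refinement. As written, the model imposes one baseline-SFS slope at one, two and four months, and Aim 4 takes its follow-up contrast from that model. The model-based variance of that contrast is inflated by roughly 0 to 11%, and that of the primary contrast at post by about 0 to 2%.

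Both ranges depend on assumed correlations and SDs. They fall to zero if slopes are constant and shrink if the SD rises over time. Because randomization is stratified on baseline SFS, the practical result is mainly a confidence interval at follow-up that is slightly too wide, which errs on the conservative side. The sample size is unaffected, and no aim's conclusion is likely to turn on this.

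**What to change.** In the primary SFS model, replace the single baseline term by baseline SFS plus baseline SFS-by-time, so that mid, post and follow-up each have their own slope. Write this into the SAP before unblinding, since adding it later would be a post hoc choice of model.

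The cost is two parameters, with 96 to 120 participants contributing, and about 0.5% more variance if the slopes turn out constant. No new data and no change in sample size are needed.

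The same term may be used for SSPA for consistency (one extra parameter), but the expected gain there is small, mostly under 1%.

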efficacy and the relationship between USS content knowledge test and social functioning change. One hundred twenty participants will be randomized to two months of individually administered USS or a matched active control training. Comprehensive assessments will occur at baseline, end of training phase, and two-month follow-up, with an additional assessment of the primary outcome and of USS content-related skill (treatment target) at training mid-point. We will additionally obtain baseline-only social function information for a normative (non-psychotic) psychiatric sample, in order to better understand and characterize the patterns of social interactions in our primary psychotic spectrum sample.

Participants:

Psychosis sample: Participants will be Veterans with a psychotic spectrum diagnosis (PSD). Specific inclusion/exclusion criteria will be as follows: diagnosis of psychotic disorder (e.g. schizophrenia, schizoaffective disorder, delusional disorder, psychosis NOS); no prior exposure to USS training, age 18 and

over; not meeting criteria for substance use disorder in past 30 days; psychiatric stability as evidenced by minimum of 30 days since last psychiatric hospitalization and since last change in psychiatric medications; no evidence of developmental disability in chart or on baseline assessment; no severe, uncorrected auditory/visual impairment; no diagnosis of medical or neurological illness known to impair brain function including dementia, presence of seizures, history of head trauma with loss of consciousness > 1hr, or clear cognitive sequelae from other illness or injury, per medical chart review; fluency in English; ability to provide legal written informed consent (i.e. the participant does not have a conservator); not currently enrolled in another treatment study targeting, or expected to impact, functioning. We hope to randomize approximately 120 Veterans into the study conditions.

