The active control (AC) intervention was selected to match USS on interaction with study staff, treatment duration and intensity, and delivery format. "Moving Forward: Overcoming Life's Challenges" is a free, web-delivered training developed by the VA as part of the Integrated Mental Health Strategy initiative to expand access, ensure quality of care, promote resilience and build better behavioral health systems. The training is based on Problem Solving Therapy⁸⁰, an evidence-based cognitive-behavioral approach to developing problem solving skills to effectively cope with stressors⁸¹. It consists of 8 modules focused on what the training is, how it may be helpful, how to solve problems under stress, steps of problem solving, and how to apply what was learned to daily life. In preparation for the current grant submission, we thoroughly reviewed and timed module content, developed procedures for how this normally self-administered program can be delivered by a study trainer in 45-60 minute sessions, and created a training manual (see Appendix). Similarly to those in the USS condition, participants in AC condition will be asked to attend two cycles of the training, for a total of approximately 16-20 sessions over two months.

Procedures for psychotic spectrum sample: Please refer to the study design and the assessments timeline (above) for detailed schematics of study procedures and assessments. Following written informed consent and baseline assessment, Veterans will be randomized (1:1) into one of two training conditions: Understanding Social Situations (USS) or a matched Active Control (AC). Training sessions will occur approximately twice per week for two months (16-20 sessions, given some expected variability in individual time to complete the training content). Training sessions will be video recorded for later fidelity ratings by research staff.

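### Trainer is absent from the SFS and SSPA models and the trainer layout is unstated, so the primary interval can be too narrow if trainers are nested in arm or their effects differ by arm.

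*Combined protocol and SAP*

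**What the plan says.** All places are in section 5, Research Plan, of the combined protocol and SAP.

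- **Delivery.** The Overview states: "One hundred twenty participants will be randomized to two months of individually administered USS or a matched active control training". The active control (AC) is "delivered by a study trainer in 45-60 minute sessions" (Matched Active Control intervention). Each arm has 16 to 20 sessions. That USS is also trainer-delivered follows from the matching of the arms on staff contact and format, and nothing contradicts it.
- **Primary model** (Analysis of Primary Outcome SFS, Aim 1). The fixed effects are arm, time, arm-by-time and baseline SFS. The only correlation structure is within person: "An unstructured covariance pattern will be used to accommodate correlation from repeated measures". Baseline predictors of dropout may be added. Trainer is not mentioned.
- **SSPA** (Aims 3 and 4). A similar mixed model is planned.
- **Elsewhere.** Randomization is stratified by baseline SFS only. The sample size treats participants as independent. Trainer is not a listed moderator, and the only sensitivity analysis described concerns missing data.
- **Not stated.** The number of trainers, how participants are assigned to them, and whether trainers are crossed with arm (each delivers both) or nested in it (each delivers one).

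**The concern.** After 16 to 20 individual sessions, participants who share a trainer may have more similar outcomes than participants who do not. A model with only within-person covariance treats all participants as independent.

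The consequence depends on the trainer layout:

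- **Nested in arm.** Differences between trainers enter the arm contrast directly, and the model's standard error does not reflect them. With one trainer per arm, no later model could separate trainer from USS.
- **Crossed and balanced.** The main trainer effect cancels. Only variation in how well a trainer does with one arm relative to the other (trainer-by-arm variation) would remain uncounted.

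AC was chosen to match USS on contact, duration and format, so that a difference can be read as an effect of USS content. That reading also needs the people delivering the two arms to be comparable, and the plan neither arranges this nor checks it.

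**Working it through.** **1. The plan's own figure.** Inputs from Justification of Sample Size: difference 9, SD 13.1, "a two-sided 0.05 significance level", 90% power, 1:1 allocation. Then d = 9/13.1 = 0.687. The noncentral t gives 89.7% power at 45 per group and 90.3% at 46, so "a sample size of 46 subjects per group will be required to detect a 9 point difference" reproduces, for independent participants. With 120 randomized and 20% dropout, 96 are analysed, or 48 per arm, and power is 91.5%.

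**2. Trainers nested in arm, no baseline adjustment.** The documents give neither the number of trainers nor the ICC (share of SFS variance lying between trainers). Both are assumed here, with one trainer per participant throughout.

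Design effect DE = 1 + (m − 1) × ICC, where m = 48 / trainers per arm. Actual type I error = 2 × [1 − Φ(1.96/√DE)].

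| Trainers per arm | m | ICC | DE | √DE | Type I error | Simulated |
|---|---|---|---|---|---|---|
| 4 | 12 | 0.02 | 1.22 | 1.10 | 7.6% | 7.4% |
| 2 | 24 | 0.02 | 1.46 | 1.21 | 10.5% | 10.2% |
| 4 | 12 | 0.05 | 1.55 | 1.24 | 11.5% | 11.9% |
| 2 | 24 | 0.05 | 2.15 | 1.47 | 18.1% | 18.4% |

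The simulated column is an unadjusted t test, 20,000 replicates.

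**3. Trainers crossed and balanced, same ICCs, two or four trainers in all.**

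- No trainer-by-arm variation: simulated type I error is 4.4% to 5.0%. Adjusting for trainer multiplies the standard error by √(1 − ICC), which is 0.990 at ICC 0.02 and 0.975 at 0.05. Power moves from 91.5% to 92.0% and 92.8%.
- Half the trainer variance as trainer-by-arm variation: 7.7% and 11.8% with two trainers (ICC 0.02 and 0.05), 6.6% and 8.0% with four.

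**4. Nested, with the planned baseline adjustment.** Let r be the correlation of pre and post SFS (not given, so assumed). Relative to SD², the variance that drives the arm contrast is V = 1 − r² + (m − 1) × ICC, while the planned model counts only 1 − r². The design effect becomes V/(1 − r²). Power uses d/√V with 48 per arm and 94 degrees of freedom.

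| Trainers per arm | ICC | r | V | V/(1 − r²) | Type I error | Power (unadjusted) |
|---|---|---|---|---|---|---|
| 4 | 0.02 | 0.5 | 0.97 | 1.29 | 8.5% | 92% (85%) |
| 2 | 0.02 | 0.6 | 1.10 | 1.72 | 13.5% | 89% (79%) |
| 2 | 0.02 | 0.7 | 0.97 | 1.90 | 15.5% | 92% (79%) |
| 4 | 0.05 | 0.7 | 1.06 | 2.08 | 17.4% | 90% (76%) |
| 2 | 0.05 | 0.7 | 1.66 | 3.25 | 27.7% | 73% (62%) |

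Baseline adjustment recovers power, but it raises the type I error when trainers are nested: it removes participant variance and leaves trainer variance in place.

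**The case against.** The strongest reply is that silence about trainers is not evidence of nesting. If every trainer delivers both arms in balance with equal effect, the interval is not too narrow. This stands. A reader might infer from the missing trainer term that trainer differences will be reported as a USS effect. The documents do not support that, because they do not say who delivers which arm. The AC training manual sits in an appendix that is not part of the text available here and might address it.

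Trainer variance may also be small. USS is manualised and highly structured, AC is built on a normally self-administered web program, and sessions are recorded for fidelity ratings. If several trainers shared one participant's sessions, clustering would be diluted. These points make a low ICC plausible but do not show it to be zero, and the fidelity ratings do not enter the outcome analysis.

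A reader might also infer that the stated 90% power is overstated. That is not established. The sample size ignores baseline adjustment, and the tables show power at or near 90% for several nested settings once it is included. Two trainers per arm at ICC 0.05 is the exception (73% at r = 0.7).

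Finally, a fixed trainer effect is no universal cure. If trainers are nested it is aliased with arm. If they are crossed without trainer-by-arm variation, its gain in precision is slight.

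**Conclusion.** The concern holds conditionally. The SFS and SSPA models have no trainer term, and the plan does not state the layout that decides whether this matters.

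- **Nested** (assumed two to four trainers per arm, ICC 0.02 to 0.05, 48 analysed per arm): type I error about 8% to 18% before baseline adjustment, and higher after it.
- **Crossed, with trainer-by-arm variation**: about 7% to 12% if half the trainer variance is of that kind.
- **Crossed, without it**: near 5%, with only 1% to 2.5% to gain in the standard error.

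Every error rate rests on assumed trainer numbers and ICCs and a single post-training comparison, not the full repeated-measures model. They show what could happen, not what the trial's error rate is. No claim about lost power is made. The plan should still be changed, because the remedy is cheap and the layout is a fact the sponsor can state.

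**What to change.** 1. State the number of trainers, how participants are assigned to them, and whether trainers are crossed with or nested in arm. Record trainer ID for every participant.
2. **If crossed:** add trainer as a fixed effect to the SFS and SSPA models, and prespecify a sensitivity model with a random trainer-by-arm effect. The main interval then covers trainer-by-arm variation only through that sensitivity model.
3. **If nested:** use a random trainer effect with Kenward-Roger degrees of freedom, not a fixed effect. Report the ICC, and state that trainer and USS effects cannot be fully separated.
4. Where feasible, have trainers deliver both arms. This changes delivery: trainers must hold two manuals, and content may carry over between arms, which the planned video fidelity ratings can check. It may be too late for participants already treated.

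The direct cost is one recorded field and one extra model. With few trainers the variance estimates will be imprecise. In the nested case the honest degrees of freedom are few, roughly 2k − 2 for k trainers per arm. At ICC 0.05 without baseline adjustment, power is then about 27% with two per arm (2 degrees of freedom) and 62% with four (6 degrees of freedom). That is a reason to settle the layout early.
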